### ***Peripheral Blood Analysis***

*(in collaboration with [name]'s laboratory in the Human Oncology Pathogenesis Program and the Immune Monitoring Core Facility at MSK)*

Rationale: We hypothesize that the impact of disrupting the PD-1/PD-L1 and CTAL-4 axes with the nivolumab/ipilimumab combination upon peripheral blood immune populations will correlate to clinical efficacy of therapy in SGC patients.

Approach: At the time points indicated in **Section 10**, peripheral blood samples will be collected: 4 CPT tubes (BD, 8-ml capacity, total blood volume collected~32 ml for PBMC purification for flow cytometric analysis) and 1 PAXgene tube (BD order #762165 or equivalent) (for purification of RNA/DNA for TCR analysis). Changes to these methods may be adapted depending upon the most recent, generally accepted protocols. Flow cytometry will be used to evaluate changes in T cell subsets at different time points. Alternative approaches to this analysis may be pursued depending upon the availability of new technologies, platforms, or approaches. Specifically, assays investigating the immunogenicity of tumoral antigens in *ex vivo* assays utilizing these collected PBMCs may be of value and will be performed to identify potential neoantigens or self antigens that are critical for mediating therapeutic efficacy.

## 10.0 EVALUATION DURING TREATMENT/INTERVENTION

All evaluations/tests and research collections may be performed up to 3 days prior to the patient being treated.

Cycle/Week of Therapy (1 cycle= 6 weeks)	Pre-Study a	Cycle 1 Week 1 i	Cycle 1 Week 3	Cycle 1 Week 5	Cycle 2+ f Week 1	Cycle 2+ f Week 3	Cycle 2+ f Week 5	Off Study g
Weeks on study	-	1	3	5	7	9	11	-
Nivolumab b		X	X	X	X	X	X	
Ipilimumab b		X			X			
Informed consent	X							
Concurrent meds	X	X d	X	X	X			X
Physical exam	X	X d	X	X	X			X
Vital signs (pulse, blood pressure)	X	X d	X	X	X			X
Weight	X	X d	X	X	X			X
Adverse event evaluation	X	X d	X	X	X			X
CBC w/diff, plts	X	X e	X	X	X	X	X	X
Comprehensive panel c	X	X e	X	X	X	X	X	X
TSH	X				X			X
Beta-HCG (serum or urine)	X i							
Request for archival tumor tissue	X							
Research blood draw	X							
Research tumor biopsies k	X k		X k					
Research peripheral blood collection j		X			X			X
Tumor measurements h	X	CT and/or MRI will be performed every 12 weeks (+/- 1 week) (or approximately every 2 cycles). Objective responses should be confirmed with a second assessment performed at least 4 weeks later.						

a: See Section 8.0 for the timing of these tests/evaluations prior to the start of therapy.

b: Study drugs will be administered at the following doses/schedules: nivolumab 3 mg/kg IV every 2 weeks and ipilimumab 1 mg/kg IV every 6 weeks. At the investigator's discretion patients can be treated with nivolumab alone after 4 cycles for safety concerns.

c: Albumin, alkaline phosphatase, total bilirubin, bicarbonate, BUN, calcium, chloride, creatinine, glucose, potassium, total protein, SGOT [AST], SGPT [ALT], sodium.

d: These Week 1 evaluations maybe performed within 3 days prior to the start of treatment.

e: These Week 1 laboratory tests may be done up to 7 days prior to starting treatment. It is unnecessary to repeat these laboratory tests if the screening assessments of the same tests were performed within 7 days prior to the first dose of therapy.

f: These columns reflect the schedule of assessments/treatment required for Cycle 2 and subsequent cycles in the weeks designated.

g: Off-study evaluation will be performed within 30 days of the patient's last dose of study drug (Exception: Patients for whom removal from the study followed a prolonged interval during which administration of study drugs was held for greater than 30 days, the off-study evaluation needs to be performed within 30 days of the patient's last physical assessment by investigator physician).

h: The treating physician may reschedule radiologyscans due to treatment delays at his or her discretion . If the patient has CT and/or MRI scans completed early for any reason (e.g. suspicion of disease progression), the next set of scans maybe ordered in 12 weeks (+/- 1 week) from that assessment. Please see Section 13.0 regarding the altered schedule of radiographic assessments required for patients being treated beyond initial evidence of tumor progression.

i. Serum or urine pregnancy test is required within 14 days of drug treatment for all women of child-bearing potential.

j: Peripheral blood samples will be collected in 4 CPT tubes (BD, 8-ml capacity, total blood volume collected~32 ml for PBMC purification for flow cytometric analysis) and 1 PAXgene tube (BD order #762165 or equivalent) (for purification of RNA/DNA for TCR analysis). The Cycle 1, Week 1 sample should be obtained prior to drug administration, but not beyond 3 days prior to the start of treatment. Subsequent samples will be obtained on Cycle 2/Week 1, Cycle 3/Week1, and then Off Study. If the collection of all 4 CPT tubes and 1 PAXgene tube are not feasible, this will not be considered a protocol deviation.

k. The first of two research biopsies will be performed anytime prior to Week 1 Day 1. Tumor tissue obtained prior to study consent or treatment as part of standard of care can also be submitted in lieu of performance of the first pre-treatment biopsy, if the Principal Investigator deems it to be of sufficient quantity/quality/timeliness. The second research biopsy will be performed prior to the administration of the second dose of ipilimumab. Exceptions regarding the timing of the second biopsy can be made at the Principal Investigator's discretion, and will not be considered a violation. Patients may be exempt from biopsy if 1) the

investigator or person performing the biopsy judges that no tumor is accessible for biopsy, 2) the investigator or person performing the biopsy feels that the biopsy poses too great of a risk to the patient, or 3) the patient's platelet count is <100,000/mcl or he/she cannot be safely removed from anti-coagulation therapy (if the anti-coagulation therapy needs to be temporarily held for the biopsy procedure). Radiologic guidance (CT, MRI or ultrasound guided) approaches and obtaining multiple cores to ensure sufficient biopsy material (at least 3 cores preferred) are allowed as long as it is considered safe for the patient. If the only tumor accessible for biopsy is also the only lesion that can be used for RECIST v1.1 response evaluation, then the patient may be exempt from biopsy. If the investigator deems a second research biopsy to be high risk after a patient has completed the first research biopsy, the patient may also be exempt from the second biopsy.

- I. If Cycle 1 Week 1 labs fall below screening requirements, the patient can start treatment at the discretion of the treating investigator if safety is not compromised.

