  - Grade 4 drug-related endocrinopathy adverse events, such as, hyper- or hypothyroidism, or glucose intolerance, which resolve or are adequately controlled with physiologic hormone replacement (corticosteroids, thyroid hormones) or glucose-controlling agents, respectively, may not require discontinuation after discussion with and approval from the Principal Investigator
- Any event that leads to delay in dosing lasting > 6 weeks from the previous dose requires discontinuation, with the following exceptions:
  - Dosing delays to allow for prolonged steroid tapers to manage drug-related adverse events are allowed.
  - Dosing delays lasting > 6 weeks from the previous dose that occur for non-drug-related reasons may be allowed if approved by the Principal Investigator.

Prior to re-initiating treatment in a participant with a dosing delay lasting > 6 weeks, the Principal Investigator must be consulted. Tumor assessments should continue as per protocol even if dosing is delayed. Periodic study visits to assess safety and laboratory studies should also continue every 6 weeks or more frequently if clinically indicated during such dosing delays.

- Any adverse event, laboratory abnormality, or intercurrent illness which, in the judgment of the Investigator, presents a substantial clinical risk to the subject with continued nivolumab or ipilimumab dosing

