#### **14.0 BIOSTATISTICS**

The primary endpoint of the study for each cohort is best overall response rate (BOR; CR+PR by RECIST v1.1). The ACC (Cohort 1) and non-ACC cohorts (Cohort 2) will be assessed separately. For ACC, our recent literature review of all systemic chemotherapy studies reported for R/M ACC patients from 1966 to 2009 revealed that these were generally small studies of variable, poor methodological quality from which definitive conclusions regarding the efficacy of chemotherapy are impossible to establish. Objective responses with cytotoxic chemotherapy were infrequent, and in 10 studies evaluating different targeted agents (imatinib, gefitinib, cetuximab, lapatinib, bortezomib (excluding the VEGR targeted TKIs)) involving 157 ACC patients, only 2 objective responses were reported (in response to high dose imatinib). Notably, there is no data addressing potential efficacy of systemic therapy beyond the first line setting in R/M ACC. The same concerns regarding trial design and modest activity with chemotherapy apply to non-ACC histologies as well. There currently is no standard therapy for SGs. Therefore, we will adopt a BOR of 5% as the null hypothesis and a BOR of 20% as desirable. A minimax two-stage design will be used for each cohort. In order to detect a difference between an unacceptable ORR of 5% and a desirable ORR of 20% with a one-sided type I error of 10% and power of 90%, at least 1 response needs to be observed among the first 18 patients enrolled in the first stage. If this is achieved, then the study will progress to the second stage in which an additional 14 patients will be accrued. In order to move to the second stage of the study, the patient response in the first stage must occur within 6 cycles (or 36 weeks (+/- 2 weeks)) of drug treatment. At the end of the trial, at least 4 responses need to be observed among a total of 32 patients of the cohort to be considered worthy of further investigation. Maximum number of patients treated in both cohorts combined would be 64 patients.

Given the length of the observation period for response, if the decision on whether to proceed to the second stage cannot be made after the first 18 patients have been enrolled, the study will not halt and patients will continue to be enrolled. In the worst case scenario, all 32 patients will have been enrolled before the decision on whether to proceed to the second

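### Scan dates may follow dosing delays at the physician's discretion, while Section 11.0 keeps assessments on protocol; the rules need reconciling, though the effect on PFS and the stage-1 gate is modest

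*Combined protocol and SAP*

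**What the plan says.** Four places in the combined protocol and SAP bear on when a patient is scanned and what depends on it.

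- Section 10.0, tumor measurement row: "CT and/or MRI will be performed every 12 weeks (+/- 1 week) (or approximately every 2 cycles"). This gives a calendar anchor and a treatment anchor side by side. Sections 1.0 and 4.2 do the same. The row adds: "Objective responses should be confirmed with a second assessment performed at least 4 weeks later".
- Section 10.0, footnote h: "The treating physician may reschedule radiologyscans due to treatment delays at his or her discretion". No maximum shift is set, and no record of the reason is asked for.
- Section 11.0, Discontinuation Criteria, in the paragraph on holds longer than 6 weeks: "Tumor assessments should continue as per protocol even if dosing is delayed".
- Section 14.0: PFS is estimated by Kaplan-Meier from the start of treatment, with no rule for late or missed scans. For the stage-1 decision, "the patient response in the first stage must occur within 6 cycles (or 36 weeks (+/- 2 weeks)) of drug treatment".

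**The concern.** Progression is recorded at the scan that shows it. If the scan moves because a dose was held, the recorded date depends on tolerability as well as on disease. Section 11.0 requires holds for many drug-related adverse events, and allows holds beyond 6 weeks for prolonged steroid tapers. Two investigators could therefore scan similar held patients on different dates and each claim to follow the protocol.

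Two results could suffer. The first is the shape of the PFS curve, in a trial without a control arm to share the artefact. The second is the stage-1 gate, because a response first seen on a postponed third scan could fall outside a 36-week limit.

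**Working it through.** **1. The plan's own design.** Inputs from Section 14.0: response rates of 5% (null) and 20% (desirable), one-sided type I error 10%, power 90%, at least 1 response in 18 to continue, at least 4 in 32 for success. Exact two-stage binomial:

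- Reject probability = sum over x from 1 to 18 of P(X = x) × P(Y ≥ 4 − x), with X binomial(18, p) and Y binomial(14, p).
- At p = 0.05 this is 0.0721; at p = 0.20 it is 0.9015. The stated error rates are met.
- False stop at stage 1 when p = 0.20: 0.8^18 = 0.018.

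**2. The stage-1 window.** Nominal scans fall at weeks 12, 24 and 36. In calendar weeks the window closes at 36 + 2 = 38, so a third scan moved by more than 2 weeks is outside it. In cycles, the window moves with the dosing delay and nothing is lost.

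For the calendar reading, let a fraction f of responses be first seen after the window, with the final count still using all responses. False stop = (1 − 0.2(1 − f))^18. For power, each term in step 1 is multiplied by (1 − f^x), the chance that at least one of x responses is in time. The documents give no value for f.

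| f | False stop at p = 0.20 | Power |
|---|---|---|
| 0 | 0.018 | 0.901 |
| 10% | 0.82^18 = 0.028 | 0.895 |
| 20% | 0.84^18 = 0.043 | 0.885 |

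Type I error falls slightly (0.071 and 0.069 for the last two rows), so the error runs toward stopping an active regimen.

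**3. PFS.** The documents give no delay rate. Assumptions: 33% of patients have scans moved (borrowed from 13 of 39 with Grade 3/4 treatment-related events on this regimen in the lung cancer study cited in Section 3.0); the move is d = 4 or 6 weeks and applies to all later scans; delay onset is uniform over weeks 0 to 24; true PFS is exponential with median 4, 6 or 9 months (4.345 weeks per month), so S(t) = 2^(−t/median).

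- On schedule, the curve equals S(24) at both week 26 and week 32, because the last scan was at week 24.
- At week 26, half of the delayed patients were last scanned at week 12 + d and half at week 12. Apparent PFS = 0.67·S(24) + 0.33·½·[S(12 + d) + S(12)].
- At week 32, delayed patients were last scanned at week 24 + d. Apparent PFS = 0.67·S(24) + 0.33·S(24 + d).

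Example, median 4 months (17.38 weeks), d = 4:

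- Week 26: 0.67 × 0.384 + 0.165 × (0.528 + 0.620) = 0.447.
- Week 32: 0.67 × 0.384 + 0.33 × 0.327 = 0.365.

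| True median | On schedule, weeks 26 and 32 | Week 26, d = 4 / 6 | Week 32, d = 4 / 6 |
|---|---|---|---|
| 4 months | 38.4% | 44.7 / 44.0% | 36.5 / 35.7% |
| 6 months | 52.8% | 58.2 / 57.6% | 51.1 / 50.3% |
| 9 months | 65.4% | 69.5 / 69.1% | 63.9 / 63.2% |

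The rise at week 26 is about 4 to 6 points, and the fall at week 32 about 1 to 3 points. A simulation of 400,000 patients per scenario agrees. It also leaves the median on the same scan date (weeks 24, 36 and 48) and raises mean recorded PFS by 0.2 to 0.5 weeks. With 20 to 50% of patients affected, the week-26 rise runs from about 2 to 9 points.

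The sign changes because a moved scan is late for progression before week 24, but early for progression between week 24 and the moved scan, which would otherwise wait until week 36.

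**The case against.** The strongest reply is that there is no contradiction. Section 11.0 has assessments continue per protocol, footnote h is part of the protocol, and the Section 11.0 sentence sits in the paragraph on holds over 6 weeks. Read together, imaging is not suspended during a hold but its timing may flex. That reading is tenable, so a reader who infers flatly opposite instructions for every delay goes too far. It does not remove the problem: on that reading Section 11.0 fixes no date, and the shift remains unlimited.

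A reader might also infer that PFS is biased upward by several points. The documents do not support this. Week 26 is close to the worst case, lying just after a planned scan; the sign reverses later in the interval. Section 14.0 names no 26-week landmark and plans no PFS test or comparison with history. Delays are not all due to toxicity, and footnote h permits a move without requiring one. The 33% is a proxy that can err either way: Grade 2 events can also cause holds, while many Grade 3 events require discontinuation instead.

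Finally, a reader might infer that postponed scans will cost the trial its stage-1 gate. The window is also expressed as 6 cycles, one timely response among 18 is enough, late responses still count toward the final 4 of 32, and accrual does not halt while the decision is pending.

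**Conclusion.** The concern stands as a wording conflict with a modest statistical consequence. The scan rules in Sections 10.0 and 11.0 must be reconciled; the conflict is clearest for holds over 6 weeks. As written, assessment timing can depend on toxicity.

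Under the stated assumptions, this distorts the PFS curve by a few points in either direction according to the week at which it is read, with the median unchanged in the 33% scenario. That stability should not be carried over to larger affected shares without recalculation.

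For the stage-1 gate, the loss is at most about 1.7 points of power (0.9015 − 0.8848) if up to 20% of responses fall outside a calendar window, and nil if cycles govern. The plan does not say which governs.

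**What to change.** 1. Delete the first sentence of footnote h.
2. Remove the two-cycle alternative from the scan interval in Section 10.0, and from Sections 1.0 and 4.2 where it recurs.
3. State that scans are due at weeks 12, 24, 36 and so on (+/- 1 week), counted from Cycle 1 Week 1, regardless of dose delays, and make Section 11.0 refer to that calendar.
4. In Section 14.0, state whether calendar weeks or cycles govern the stage-1 window. It would help to say there also whether the confirmatory scan must fall inside it: in calendar weeks, a response first seen at week 36 could be confirmed no earlier than week 40, against a limit of week 38.

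These changes add no scheduled scans. The cost is that some scans will not coincide with a dosing visit.

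The provision in footnote h that restarts the 12-week count after an early scan can stay. If it were removed too, the amendment should say that this can add a scan: a patient scanned early at week 8 may now wait until about week 20, but under a fixed calendar would also be due at week 12.

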## 11.0 TOXICITIES/SIDE EFFECTS

There will be no dose modifications permitted. Dose reductions or dose escalations are not permitted.

### ***Management Algorithms for Immuno-Oncology Agents***

Immuno-oncology (I-O) agents are associated with adverse events (AEs) that can differ in severity and duration than adverse events caused by other therapeutic classes. Nivolumab and ipilimumab are considered immuno-oncology agents in this protocol. Management algorithms have been developed to assist investigators in assessing and managing the following groups of adverse events: Gastrointestinal, Renal, Pulmonary, Hepatic, Endocrinopathies, Skin, and Neurological (see Appendix 3; these are guidelines, not required interventions).

Early recognition and intervention are recommended according to the management algorithms; and in addition include ophthalmologic evaluations for any visual symptoms in order to evaluate for nivolumab or ipilimumab related uveitis.

The recommendations are to follow the algorithms in the nivolumab investigator brochure for immune related events; while the ipilimumab investigator brochure contains similar algorithms, the algorithms in the nivolumab brochure have been aligned to accommodate combinations as well as nivolumab monotherapy. (see also Appendix 3; IB algorithms and Appendix 3 instructions are guidelines, not required interventions).

Therefore, the algorithms recommended for utilization are included here for reference. Additional details on the safety of nivolumab and ipilimumab, including results from clinical studies, are available in the IB.

### **Dose Delay Criteria**

**Because of the potential for clinically meaningful nivolumab-related AEs requiring early recognition and prompt intervention, management algorithms have been developed for suspected AEs of selected categories.**

Dose delay criteria, treatment resumption criteria, drug discontinuation criteria, and management algorithms described in this section and Appendix 3 are applicable for drug-related adverse events (adverse events that are possibly, probably, or definitely related to nivolumab, ipilimumab, or both). All study drugs must be delayed until treatment can resume.

Nivolumab and ipilimumab administration should be delayed for the following:

- Any Grade  $\geq$  2 non-skin, drug-related adverse event with the exception of fatigue, medically managed hypothyroidism or hyperthyroidism, tolerable Grade 2 AEs (except for grade 2 uveitis discussed below), and Grade 2 laboratory abnormalities other than Grade 2 creatinine, AST, ALT, and/or total bilirubin abnormalities
- Grade 2 drug-related creatinine, AST, ALT, and/or total bilirubin abnormalities.
- Any Grade 3 skin, drug-related adverse event
- Any Grade 3 drug-related laboratory abnormality, with the following exceptions:
  - Grade 3 or 4 lymphopenia or asymptomatic amylase or lipase abnormalities do not require a dose delay

- Grade  $\geq$  3 AST, ALT, total bilirubin will require dose discontinuation
- Any adverse event, laboratory abnormality, or intercurrent illness which, in the judgment of the investigator, warrants delaying the dose of study medication.

### **Criteria to Resume Treatment**

Subjects may resume treatment with study drug when the drug-related AE(s) resolve to Grade  $\leq$  1 or baseline value, with the following exceptions:

- Subjects may resume treatment in the presence of Grade 2 fatigue
- Subjects who have not experienced a Grade 3 drug-related skin AE may resume treatment in the presence of Grade 2 skin toxicity
- Subjects with Grade 2 AST, ALT, and/or total bilirubin abnormalities may resume treatment when laboratory values return to baseline and management with corticosteroids, if needed, is complete
- Subjects with combined Grade 2 AST/ALT AND total bilirubin values meeting discontinuation parameters (below) should have treatment permanently discontinued
- Drug-related pulmonary toxicity, diarrhea, or colitis, must have resolved to baseline before treatment is resumed. Subjects with persistent Grade 1 pneumonitis after completion of a steroid taper over at least 1 month may be eligible for retreatment if discussed with the Principal Investigator.
- Drug-related endocrinopathies adequately controlled with only physiologic hormone replacement may resume treatment. Adrenal insufficiency requires discontinuation regardless of control with hormone replacement.

If the criteria to resume treatment is met, scheduling of subsequent will be determined by treating investigator and PI.

Continuing treatment with both ipilimumab and nivolumab is preferred. However, resumption of therapy with just one drug (either nivolumab or ipilimumab) may be considered if 1) the investigator makes the judgement that proceeding with only one drug is necessary to possibly avoid recurrence of an adverse event that would require further dose delay, and 2) it is discussed with the Principal Investigator.

If treatment is delayed  $>$  6 weeks, the subject must be permanently discontinued from study therapy, except as specified in discontinuation section.

